#### 8.3.4. Potential covariates/subgroups

Subgroups of interest include:

- Demographic groupings: age categories, sex.
- Patients who decrease their consumption of rescue and/or controller medications during the follow-up period versus those who do not.
- Comorbidity groupings: COPD, diabetes

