## Drug consumption

All drug consumption will be analyzed, with specific attention given to (i) mepolizumab, (ii) corticosteroids (oral/IV/systemic, inhaled, topical, etc), asthma-specific medications (selective beta-2-adrenoreceptor agonists, adrenergics in combination with corticosteroids or other drugs, anticholinergics, adrenergics for systemic use, xanthines, leukotriene receptor antagonists, other systemic drugs for obstructive airway diseases, etc), and diabetes-related medications (buiguanides, insulin, etc). Drugs demonstrating significant changes in cumulative dose between the baseline and exposure periods (if any in addition to mepolizumab) will be identified.

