#### Costs

Cumulative per-beneficiary costs (including all health care resource uses and government benefits) will be described and contrasted between the baseline and exposure periods. This will be performed at several levels: (i) all costs regardless of source or potential link with diagnoses, (ii) costs due to mepolizumab, (iii) costs that can be associated with asthma-specific care, (iv) costs that can be associated with the monitoring and care for certain key comorbidities (diabetes, bone density/osteoporosis).

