### Subpopulations of interest

Sub populations of interest and subject to comparative analyses include sex, age groups, beneficiaries with versus without indicators of severe asthma, uncontrolled asthma, chronic obstructive pulmonary disease, and diabetes (identified via the prescription of specific drugs, hospitalization diagnoses, assessments or combinations thereof).

Objectives	Endpoints
Primary	
To estimate the change in associated costs for the first year of treatment	
 
Total health care costs for the year preceding the initiation of mepolizumab, as well as for the year after.
 

Secondary	
To describe the initial one-year changes in health resource use before and after the initiation of mepolizumab treatment	
 
Cumulative estimates for health resource use and associated costs for the year preceding the initiation of mepolizumab, as well as for the year after.
 

Tertiary/Exploratory	
To further characterize rates of change in health resource usage and/or costs in subpopulations of interest	
 
Sub populations of interest and subject to comparative analyses include sex, age groups, beneficiaries with versus without indicators of severe asthma, uncontrolled asthma, chronic obstructive pulmonary disease, and diabetes (identified via the prescription of specific drugs or combinations thereof).
 

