# 7. Study Assessments and Procedures

# 7.1. Efficacy Assessments

Not applicable. No efficacy assessments will take place during this retrospective, observational study. The notion of efficacy is nevertheless represented by an expected decrease in the use of asthma rescue medications during the mepolizumab exposure period.

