### 8.3.1.1. Mepolizumab exposure

Mepolizumab exposure will be characterized by cumulative numbers of injections and dosage.

Medication persistence is defined as the duration from T0 to the discontinuation of therapy (Cramer et al. 2008)(or the end of follow-up for the present study).

The proportion of days of follow-up covered (PDC) by mepolizumab (or the anologous medication possession ratio for dispensations) will also be calculated as the best available proxy for adherence and an important covariate for analyses or defining subgroups.

If mepolizumab is administered during a hospital stay, the dispensation might not be captured. This possibility will be explored by juxtaposing uncovered (non-PDC) time with hospital stays and investigating two extreme hypotheses: either all such stays contained the missing administration, versus no such stays contained the missing administration. This will provide minimum and maximum possible ranges for mepolizumab exposure.

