#### 8.3.2. Comparing health resource usage and costs before and after T0

Descriptive statistics for the different types of health resource usage and their associated costs will be calculated for both the baseline and exposure periods. Differences between the two study periods will be presented with their 95% confidence intervals. Statistical techniques for paired data (paired t-tests, paired Wilcoxon tests) will be used to compare variables between the two periods. Potential covariates/subgroups-of-interest will be tested via interaction terms (covariate x period interactions) in mixed models with patients as fixed effects or via regression models explaining the change in resource use ( $\Delta$ baseline period-exposure period). Due to the descriptive and exploratory nature of this study, results will be presented with and without the application of a False Discovery Rate (FDR) correction for multiple testing.

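### A subgroup defined by a post-T0 fall in medication is tested against outcomes that contain that fall, and PDC, where related to costs that include mepolizumab, largely returns the drug's own cost

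*Protocol*

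**What the plan says.** Section 8.3.4 of the protocol names three kinds of subgroup: demographic groups, comorbidity groups (COPD, diabetes), and "Patients who decrease their consumption of rescue and/or controller medications during the follow-up period versus those who do not". It does not say whether the decrease is measured against the baseline year or within follow-up.

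On testing, section 8.3.2 states: "Potential covariates/subgroups-of-interest will be tested via interaction terms (covariate x period interactions"). The models are mixed models or, alternatively, regressions of the baseline-to-exposure change. The endpoint table in section 8.3.1.3 applies the primary-endpoint strategy to subgroups.

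Medication use is also an outcome. Section 2 (Drug consumption), repeated in section 5.7, says: "Drugs demonstrating significant changes in cumulative dose between the baseline and exposure periods (if any in addition to mepolizumab) will be identified". Section 7.1 describes the study's notion of efficacy as "an expected decrease in the use of asthma rescue medications during the mepolizumab exposure period". The primary endpoint in the section 2 table is "Total health care costs for the year preceding the initiation of mepolizumab, as well as for the year after", and the Costs paragraph counts everything: "Cumulative per-beneficiary costs (including all health care resource uses and government benefits) will be described and contrasted".

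On adherence, section 8.3.1.1 calls the proportion of days covered (PDC) the "best available proxy for adherence and an important covariate for analyses or defining subgroups"; section 5.6 says much the same. PDC is not in the section 8.3.4 list.

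**The concern.** Membership of the decreaser group is known only after T0 and is read off an outcome. Ordinary year-to-year variation sorts patients into those whose use happened to fall and those whose use did not. The first group will then show a larger fall in medication use, and in any cost that moves with it, even if mepolizumab does nothing. A significant interaction could be published as evidence that responders save money, which this comparison cannot show.

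PDC raises a related problem. Mepolizumab is paid for only after T0, in proportion to doses dispensed, so a regression of total-cost change on PDC contains the drug bill on one side and its driver on the other. Nothing in the protocol keeps mepolizumab cost out of such an analysis or limits tested covariates to those known at T0.

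**Working it through.** **Inputs from the protocol.** Section 8.1 gives 29 × 97 = 2813 patients and at least 90% power for effect sizes above 0.063; section 8.3.1 gives a two-sided 5% level. The protocol gives no SD, correlation or drug price, so those below are assumptions, shown as ranges.

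**The plan's own figure.** Paired t-test power at d = 0.063 and n = 2813 is 91.6%; with the Wilcoxon efficiency factor 3/π it is 90.4%. The stated figure reproduces. A comparison of two equal halves has standard error √(4/2813) = 0.0377 SD of the change, so its 90% detectable difference is (1.960 + 1.282) × 0.0377 = 0.122 SD.

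**Decreasers, no drug effect.** Assume a normal change score centred at zero, split at zero, with the decrease taken against baseline.

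- Defining medication: the group difference is 2√(2/π) = 1.596 SD of the change, whatever the between-period correlation ρ. In single-period SDs, multiply by √(2(1−ρ)): 1.89 at ρ = 0.3, 1.60 at 0.5, 0.71 at 0.9. Simulation at n = 2813 rejected in 100% of runs.
- Total cost: if medication change and cost change correlate at c, the difference is 1.596 × c SD of the cost change, and z is that divided by 0.0377.

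| c (assumed) | Difference (SD of change) | z |
|---|---|---|
| 0.1 | 0.16 | 4.2 |
| 0.2 | 0.32 | 8.5 |
| 0.3 | 0.48 | 12.7 |

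Simulated rejection was 98–100% for c from 0.1 to 0.5. At c = 0 it was 3.5–9% (200 runs per setting), close to nominal. The expected z reaches 1.96 at c = 1.96 × 0.0377 / 1.596 ≈ 0.05.

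**PDC, no effect on other costs.** Let A be the annual mepolizumab cost at full coverage. Change in total cost = A × PDC + other change, so the slope on PDC is A by accounting. With an assumed PDC SD of about 0.17 and other-cost change having SD s × A, expected z ≈ 0.17 × √2813 / s = 9.0 / s. Simulated rejection was:

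- s = 0.5 to 1: 100%
- s = 2: 99%
- s = 3: 85%
- s = 5: 43%

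With mepolizumab cost removed, the slope fell to between −0.03 and 0.02 of A and rejection to 3–5%.

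**Is a pre-T0 medication subgroup free of this?** Not entirely. A median split on baseline use separates the groups by 1.596 SD at baseline. With ρ = 0.5 they then differ by 1.596 × 0.5 = 0.80 SD in change through regression to the mean. At a cost correlation of 0.3 that is 0.24 SD of cost change, z about 6.3. The artefact is half as large, but still present.

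**The case against.** The strongest reply is that this work is exploratory. The section 2 table places subgroup analyses at the tertiary level, its list does not include decreasers, section 8.3.4 is headed as potential subgroups, and section 8.3.2 stresses the study's descriptive purpose. All of that stands and limits the severity. It does not make a circular test informative. The false discovery rate correction does not help either, because the problem is bias rather than multiplicity. Describing how costs move in patients who reduce rescue medication is a fair aim; the objection is to testing it.

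A reader might go further than the protocol supports in four ways:

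- **That the cost interaction is large and significant by construction.** This is certain only for the defining medication. For total cost it rests on an unstated correlation. At c = 0.1 the difference is 0.16 SD, below the 0.2 that section 8.1 calls small, and at zero correlation there is no artefact.
- **That PDC is mechanically tied to every outcome.** The accounting link exists only where the outcome contains mepolizumab cost. For hospitalizations, consultations and other drugs the issue is confounding and reverse causation.
- **That the primary cost difference will be adjusted for PDC.** No section says so. PDC is called an important covariate without naming an outcome, and the Costs paragraph already separates mepolizumab cost.
- **That death lowers PDC.** PDC is a proportion of follow-up days, and section 4.2 lets follow-up end at death, so the denominator shortens too.

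**Conclusion.** The point holds in this form and should be fixed. For the defining medication, the decreaser interaction is circular: 1.6 SD of the change with no drug effect. For total cost it is biased by about 0.16–0.48 SD (z about 4–13 at n = 2813) if the correlation of changes is 0.1–0.3. Those sizes assume a normal change score, an even split and a decrease measured against baseline. If the decrease is instead measured within follow-up, they do not carry over directly, but membership is still defined after T0. For outcomes containing mepolizumab cost, PDC largely returns the drug's own cost; how often that reaches significance depends on the spread of other costs.

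A reader might infer that the main result is compromised. It is not: the whole-cohort before/after comparison of total cost uses neither variable. The damage is confined to exploratory subgroup and covariate results.

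**What to change.** - **Section 8.3.4:** take the medication-decrease grouping out of the interaction tests. Report it descriptively only, say what the decrease is measured against, and show costs excluding the defining drugs.
- **Sections 8.3.1.1 and 8.3.2:** relate PDC only to outcomes that exclude mepolizumab cost, using the separation already planned under Costs, and interpret the result as association. A month-6 landmark (early PDC against later non-mepolizumab costs) is optional; it uses only part of the exposure year and remains open to confounding by adherence.
- **Tested subgroups:** limit them to characteristics known at T0: sex, age, and the COPD, diabetes and severe or uncontrolled asthma indicators, each computed from pre-T0 data.
- **Add a caution:** subgroups defined by high baseline medication or resource use are subject to regression to the mean in a before/after design, so their interactions must not be read as treatment effect.

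The cost is protocol wording and minor programming. No new data are needed, and the change is best made before extraction.

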# 10. Appendices

# **Appendix 1: Abbreviations and Trademarks**

CEREES: Comité d'Expertise pour les Recherches, les Études et les Évaluations dans le domaine de la Santé; Evaluation committee for research, studies and evaluations in the field of health

CNAMTS: Caisse Nationale d'Assurance Maladie des Travailleurs Salariés; French National Health Insurance for Employees

CNIL: Commission Nationale de l'Informatique et des Libertés. The French data protection commission

COPD: chronic obstructive pulmonary disease

CS: corticosteroid

EnCEPP: European Network of Centers for Pharmacoepidemiology and Pharmacovigilance

ICS: inhaled corticosteroid

LABA: long acting beta antagonist

OCS: oral corticosteroid

PDC: proportion of days of follow-up covered by mepolizumab

PMSI: Programme de Médicalisation des Systèmes d'Information. A French national hospitalizations database.

SABA: short acting beta antagonist

SNDS: Système National des Données de Santé. National Health Data System in France.

SNIRRAM: Système National d'Information Inter Régimes de l'Assurance Maladie. The main national claims database in France.

T0: The time of the first mepolizumab administration.

# **Appendix 3: Study Governance Considerations**

## **Regulatory and Ethical Considerations**

This study will be performed exclusively using French national claims data - Research Not Involving Human Subjects - and corresponds to a standard request for SNDS data access.

In accordance with French regulations, study authorization will be sought with the National Institute of Health Data (*Institut des Données de Santé*), the CEREES (*Comité d'Expertise pour les Recherches, les Études et les Évaluations dans le domaine de la Santé*; Evaluation committee for research, studies and evaluations in the field of health) and the French data protection commission (*Commission Nationale de l'Informatique et des Libertés*) before commencement. We will also seek ethical approval from the Institutional Review Board at the University Hospitals of Montpellier, Montpellier, France. In addition, the study will be registered prior to data extraction with the following entities: (i) clinicaltrials.gov (public disclosure), (ii) the open science framework (public disclosure), and (iii) www.encepp.eu (European Medicines Agency).

#### **Informed Consent Process**

Not applicable.

#### **Data Protection**

SNDS data are accessible only by specially trained and qualified individuals.

## **Publication Policy**

- The results of this study may be published or presented at scientific meetings.
- Authorship will be determined by mutual agreement and in line with International Committee of Medical Journal Editors authorship requirements.

#### **Dissemination of Clinical Study Data**

Only aggregated statistics (analysis results) will be disseminated. French regulations do not permit re-use or dissemination of the raw data.

#### 1- Data transfer process:

No individual data will be exported from the CNAMTS secured platform. Only the associated/aggregate data and the result tables will be exported from the CNAMTS secured platform.

## 2- Access to traceability after connections:

CNAMTS will be able to track all connections of qualified people made in the CNAMTS secured platform within the scope of the study.

## 3- Data preservation:

The project dossier located in the CNAMTS platform will be archived and stored by CNAMTS. The aggregated data extracted from the analyses and the result tables will be stored for a period of 3 years after the publication of the results, according to the request sent to CNIL.

#### 4- Non-reuse of data:

The investigators will undertake not to reuse the individual data handled in the CNAMTS secured platform outside the scope of the present project.

## **Data Management**

Data-management and analysis will be performed only after favorable opinion from CEREES, authorization from CNIL, and signature of the convention with CNAMTS (*Caisse Nationale d'Assurance Maladie des Travailleurs Salariés;* French National Health Insurance for Employees) to access the SNDS data required for the study.

Data-management and analyses will be performed by authorized and appropriately trained staff at the University Hospitals of Montpellier (Department of Medical Information) to access the data of the SNDS.

Data-management and analyses defined in the protocol will be carried out within a secured platform (SAS® software) from an extraction carried out by CNAMTS. Access to the SNIIRAM data requires therefore an *a priori* definition of a selection algorithm (for e.g. based on based on medication codes UCD 9413850 // code CIP\_C13 3400930038352) for patients needed to perform the study and a listing of the variables required.
